6.4 INTERVENTION COMPLIANCE

[figure not shown]
[figure not shown]
Implementation Processes: Importantly, this is a quality improvement intervention that will be implemented flexibly by hospital staff and not a rigid protocol to which they must comply. The Chief Patient Safety Officer ([name]), will oversee implementation of the SAFE Loop, given his extensive prior experience implementing other performance improvement interventions. *Planning:* During year 1, the research team will refine the implementation plan, which considers stakeholders' needs, tailors the SAFE Loop for subgroups (e.g., nurses vs. unit managers), employs appropriate communication channels (e.g., daily nursing huddles), and tracks progress toward milestones. *Engaging:* Engagement is fundamental to the SAFE Loop, particularly nurses' input on medication safety problems, participation in "mini-root-cause analyses," and receipt of feedback. *Executing:* SAFE Loop Team members will reinforce the SAFE Loop via stimulated reporting and feedback. Nursing Unit Managers will serve as local implementation leaders, and each nursing unit has one or more additional nurses designated as Safety Representatives who will assist with this process. *Reflecting and Evaluating:* We will perform a detailed qualitative analysis of implementation.

The SAFE Loop intervention is designed to shape but not constrain or determine or control systems of medication management on each nursing unit. These systems of medication management, in turn, influence but do not constrain or determine how individual clinicians provide care to individual patients. The care provided to individual patients can, unfortunately, involve medication errors. Medication

errors are problems with the ordering, dispensing, administration, or monitoring phases of medication therapy. Patient outcomes resulting from medication errors are influenced by the errors themselves as well as patient characteristics including the reason for hospitalization, the set of medications, age, gender, comorbidities, and diverse other factors.

Under the SAFE Loop, the goal is to have nurses use incident reports to identify problems with systems of care on the nursing units and then develop and implement changes to those systems of care that reduce the likelihood of medication errors. As indicated by the diagram below, the SAFE Loop intervention has the potential to influence systems of medication therapy, care for individual patients, and patient outcomes, but these are not under direct investigator control.

Relationship between Intervention, Systems of Care, Care for Individual Patients, and Outcomes

6.5 CONCOMITANT THERAPY

Not Applicable

6.5.1 RESCUE MEDICINE

Not Applicable

7 STUDY INTERVENTION DISCONTINUATION AND PARTICIPANT DISCONTINUATION/WITHDRAWAL

7.1 DISCONTINUATION OF STUDY INTERVENTION

The DSM will be able to interrupt the trial if there are serious concerns about data safeguarding or safety based on potential adverse events or other information, and if there have been any adverse events (particularly serious events). The study team will work with the DSM to develop rules for stopping the trial, based on the occurrence of severe adverse events.

Discontinuation of the SAFE Loop intervention does not necessarily mean discontinuation of the study, and remaining study procedures should be completed as indicated by the study protocol. If a clinically significant finding is identified in a participant or one arm (including, but not limited to changes from baseline) after enrollment, the investigator or qualified designee will determine if any change in participant management is needed.

7.2 PARTICIPANT DISCONTINUATION/WITHDRAWAL FROM THE STUDY

The SAFE Loop intervention is implemented at the level of the nursing unit. Additionally, the nursing units choose how to modify systems of medication therapy to improve safety, and those local changes can be considered hospital quality improvement interventions. As such, individual nurses and patients do not have the ability to withdraw from the study. However, nurses can choose not to engage in SAFE Loop activities such as filing incident reports on Target Medication Events. Nurses can also decline to respond to the survey under Aim 2. No data are collected directly from patients.

7.3 LOST TO FOLLOW-UP

Not applicable. We will have complete data on all patients who receive care on the study nursing units. If nurse choose not to complete the survey, this will not constitute “loss to follow-up.”

8 STUDY ASSESSMENTS AND PROCEDURES

8.1 EFFICACY ASSESSMENTS

Methods for Aim 1: Incident Reporting Practices

A. Measures: There are two key outcome measures and several descriptive measures. One key outcome measure is the *rate per 1000 patient-days of incident reports addressing one of the Target Medication Events*. Ten nursing units will implement the SAFE Loop, leading to 10 Target Medication Events total.

The primary outcome measure will be *the number of system plus human factors per incident report*. In industries where incident reporting has been effective, obtaining insights into contributing system and human factors has been the purpose of reporting. To *characterize system and human factors*, we will use the Human Factors Analysis and Classification System for Healthcare (HFACS-Healthcare).⁴⁴ Introduced in 2001, the HFACS has widely been used to analyze incidents in diverse industries internationally.⁴⁴⁻⁴⁷ More recently, HFACS developers adapted it for use in healthcare settings.⁴⁸ HFACS-Healthcare lists 21 categories of contributing factors within 4 tiers (**Table 6**).⁹ We will also examine the number and diversity of factors reported.

Table 6: Incident Report Characteristics		
Contributing Factors (HFACS, 4 tiers)		
Organizational influences (system factors)		
	Unsafe supervision (system factors)	
	Preconditions for unsafe acts (system)	
		Unsafe acts (human factors)
Severity (NCC MERP, 9 Categories)		
A: Safety hazard (did not involve patient)		
B: Event did not reach patient		
C: Event reached patient, no harm		
D: Monitoring/intervention to prevent harm		
E: Temporary harm requiring intervention		
F: Temporary harm, prolonged hospitalization		
G: Permanent harm		
H: Intervention to sustain life		
I: Death		
Preventability (Brook et al.)		
Definitely or probably preventable		
Definitely or probably not preventable		
Uncertain/unable to determine (added)		

Descriptive Measures: Patient factors also represent opportunities to improve care. To classify *patient factors*, we will use categories from prior work.⁴ Experts consider severity and preventability when prioritizing incidents for follow-up and action.⁴⁹ To classify *severity*, we will use the NCC MERP Medication Error Index.⁵⁰⁻⁵² To classify *preventability*, we will adapt an existing scale.⁵³

Data Collection: Analysts with clinical experience (e.g., nursing, pharmacy) and training in HFACS-Healthcare will manually review incident reports related to medication issues. Pairs of analysts will independently judge whether each incident matches one of the definitions of Target Medication Events, extract information related to the measures above, and then meet to discuss and reach consensus. A human factors expert ([name]) will adjudicate any ties. Analysts will be blinded to nursing unit, time period, and study arm. Data collection instruments will be adapted from our prior work.^{4,9,54} As part of training, analysts will practice on at least 30 sample reports, consulting with each other and the human factors expert until scores are consistent. To evaluate reliability, we will calculate Cohen’s Kappa for 10% of records.

Methods for Aim 2: Nurses’ Attitudes toward Incident Reporting

Measures: The planned outcome measures include two composite measures from the AHRQ Hospital Survey on Patient Safety (SOPS) Culture™, Version 1.0 (English). AHRQ developed the survey in 2004 to assess the perspectives of frontline providers and staff on patient safety, error, and event reporting. Since then, hundreds of hospitals across the U.S. and internationally have used it. The survey has moderate-to-strong validity and reliability,⁵⁵ and the items and dimensions are psychometrically sound at the individual, unit, and hospital levels.⁵⁶ A 2015 systematic review found associations between Hospital SOPS scores and patient outcomes at hospital and nursing-unit levels of analysis.⁵⁷ Scores represent percentages (range 0-100%, higher is better). Changes in overall Hospital SOPS scores of 8.6 percentage points (range, 6.5-10.6) have been associated with changes in practices by hospital leaders.⁵⁸

Table 8: Hospital Survey on Patient Safety (SOPS) Culture, Including Data from Study Site (CSMC) and Nationally		
12 Composite Measures	CSMC	National
Feedback & Communication About Error	75%	68%
Frequency of Events Reported	72%	67%
Communication Openness	63%	64%
Handoffs & Transitions	52%	46%
Management Support for Patient Safety	72%	73%
Nonpunitive Response to Error	35%	44%
Organizational Learning	83%	73%
Overall Perceptions of Patient Safety	70%	66%
Staffing	49%	53%
Supervisor Expectations & Actions	74%	79%
Teamwork Across Units	66%	61%
Teamwork Within Units	84%	82%

The survey takes 10-15 minutes to complete and includes 42 items used to derive 12 composite measures (**Table 8**), 2 single-item measures, and respondents' backgrounds (unit, staff position, interaction with patients, years of experience in current profession, hospital, and current nursing unit). Most items are scored on a scale from 1 (strongly agree) to 5 (strongly disagree). Creating composite scores involves: (1) inverting the scales of any negatively worded items, (2) identifying positive responses (1 or 2); (3) calculating the percent of responses that were positive for each item (excluding missing values), and (4) averaging the percent positive across all items within a composite measure.

The two composite measures we plan to use are directly relevant to incident reporting and likely to be responsive to system-level changes. *Feedback and Communication About Error* includes three items: staff are informed about errors, discuss ways to prevent errors, and are given feedback about changes implemented. The *Frequency of Events Reported* also includes three items: staff report mistakes that are caught before affecting the patient, with no potential to harm, and that could harm but did not. In a prior analysis from three nursing units at three different hospitals, scores on these two composite measures were correlated ($\rho=0.56$) but factor analyses indicated that they captured distinct concepts (loaded separately). Respectively, Cronbach α values for these measures were 0.77 and 0.78 among nurses, demonstrating good internal consistency.⁵⁵

B. Data Collection: Cedars-Sinai routinely surveys staff every two years using the Hospital SOPS. For the study, we will survey ~1980 eligible nurses on study nursing units twice via 4 total deployments of the full Hospital SOPS during two-week intermissions between study periods (Section 3A). To identify eligible nurses, we will obtain staffing databases including names, email addresses, title/position, percent effort, dates of work on the unit, and work schedule. At least 85% of nurses on study units will be eligible. Two weeks before deployment, we will send email notices to expect the survey and a researcher will visit nursing units to reinforce survey completion. The survey will be delivered via REDCap using a weblink embedded in an email. During each deployment, we will deliver the survey three times. We will incentivize completion at the individual (lotteries for iPads) and unit levels (gift baskets of snacks for response rates >65%). To minimize detection bias, the survey will not refer to the SAFE Loop intervention. To avoid having incomplete outcome data, we will monitor survey response rates and make adjustments to procedures as needed.

Methods for Aim 3: Rates of Target Medication Events

A. Measures: The primary outcome will be the *rate per 1,000 patient-days of Target Medication Events (preventable plus potential adverse drug events)* selected by the 10 nursing units in Groups 1 and 3. We will also examine the rate of events involving harm. We will define events as in prior research (**Table 10**).^{38,61,62}

Table 10: Medication Event Definitions		Examples
ADE (NCC MERP severity E-I)	A patient injury* resulting from a medical intervention related to drug(s).	A rash due to an antibiotic.
Preventable	An adverse drug event due to a medication error. †	A rash due to an antibiotic given despite known allergy.
Non-preventable	An adverse drug event not due to an error.	A rash occurring after first exposure to an antibiotic.
Potential ADE	A medication error that had the potential to cause injury but did not.	
Intercepted (NCC MERP B)	A medication error that was detected and stopped before the patient received the medication.	A pharmacist filling orders discovers a known allergy and prompts the prescriber to switch antibiotics.
Non-intercepted (NCC MERP C-D)	A medication error in which the patient received the medication but did not to experience harm.	A patient with a known allergy to an antibiotic receives the drug anyway but does not develop a rash.

*An injury is an unintended consequence of care that negatively affects a patient's health and/or quality of life. † A medication error is an error anywhere in the process of drug ordering, dispensing, administration, and monitoring.

Descriptive Measures: We will characterize event severity/harm (NCC MERP categories), medication class (e.g., cardiovascular, diabetes, etc.), and route of administration (intravenous, oral, etc.). We will classify any errors by stage in drug therapy (ordering, dispensing, administering, monitoring), profession(s) involved (physician, pharmacist, nurse, other), and error types (allergy, drug-disease interaction, drug-drug interaction, drug-lab interaction, duplicate therapy, therapeutic omission, concentration, duration, route/dosage form, dose/frequency/rate, wrong medication, wrong patient, wrong timing, incomplete order).^{5,6,38,61} We will assess which events are Target Medication Events used by Group 1 and 3 nursing units (yes, no; and which unit).

B. Data Collection: The nursing units will implement mitigation plans designed to prevent Target Medication Events toward the end of the SAFE Loop implementation (Section 2B), which means that medication events will not start to fall until after that. Accordingly, we will monitor medication events during a baseline period, the implementation period, and 6-month follow-on period after implementation (Section 3A). To identify medication events, we will randomly sample 1,520 hospitalizations divided equally between the four study groups and the baseline and follow-on periods. (We will exclude the emergency department from Aim 3).

To detect medication events, we will employ the widely accepted Trigger Tool Method by Institute for Healthcare Improvement. It involves two stages: (1) nurses systematically screen medical records for “triggers” (clues that an event occurred) and write synopses of possible events, and (2) physicians review synopses to confirm and classify them. Many studies have used these methods, including studies by Dr. **[name]**.^{5,6,38,61-64}

Screening: Research nurses will search for several types of triggers including the use of medications that can counteract other medications (e.g., naloxone), abnormal lab results (e.g., serum glucose <50 mg/dL), clinical events (e.g., rash), abrupt cessations of medication, and transfers to a higher level of care.⁵² To increase our ability to detect potential ADEs, we will add an additional “trigger”: events in the Cedars-Sinai “Ivents” database, where pharmacists routinely record changes to medication therapy made to reduce the risk of harm (overseen by Dr. **[name]**). Ivents reports are distinct from voluntary incident reports (we will not include regular incident reports). Two research nurses will perform these screenings, blinded to study arm. To train the nurses, we will adapt training manuals and procedures from the Institute for Healthcare Improvement and our prior research.^{5,6,52} Manuals will include descriptions of the Trigger Tool method, Ivents reports, and variables employed in classifying the medication events. Through a 3-day in-person training session, nurses will become familiar with the manuals, ask questions, review 3 sample charts with supervision (by [name]), review an additional 5 to 7 sample charts independently, and then meet with the trainer to assess proficiency. During data collection, quality monitoring and training reinforcement will occur in two ways (1) the research nurses will submit questions and maintain a log of trainers’ responses, and (2) physician reviewers will ask for clarifications when the event synopses lack essential information. To obtain potential covariates for use in regression models, nurses will also extract patient age, gender, race, ethnicity, discharge diagnosis codes needed to score the Elixhauser comorbidity index, and primary and secondary payer. To ascertain reliability (Cohen’s kappa statistics), a randomly chosen 10% of medical records will undergo duplicate review.

Classification: Two physicians will independently review each synopsis, employing a standardized rating form that includes the variables above. Next, they will meet to discuss responses. When there are discrepancies, physicians may ask the research nurses for additional information or involve a third physician to break ties. To ensure blinding, synopses will not include identities of patients, clinicians, or

nursing units. For training, physicians will receive similar manuals as the nurses and score 20 sample events with an experienced reviewer ([name]). We will select 10% of synopses to calculate interrater reliability (Cohen's kappa).

Qualitative Analysis of Implementation: If the SAFE Loop improves outcomes, understanding how and why it worked will enable the intervention to be improved and adapted for use at other hospitals as well as at Cedars-Sinai. Similarly, if the SAFE Loop is ineffective, insights into its limitations will reveal how incident reporting systems could be improved through other types of changes.

A. Data Collection: After SAFE Loop implementation, we will conduct one-on-one in-person interviews with 10 Nursing Unit Managers and 22 frontline nurses. This sample size will enable us to perform purposive sampling to acquire broad representation by randomization block, study group, and nursing unit. Interviews will occur in locations convenient to interviewees, last approximately 30 minutes, and be audio recorded (with permission). We will recruit interviewees by visiting nursing huddles.

Participants will be entered into a lottery for an iPad. We will use a semi-structured interview guide with open-ended questions and follow-up probes to examine several topics, including: fidelity to SAFE Loop as planned, adaptations to SAFE Loop, SAFE Loop "dose" (e.g., did nurses learn about it once or several times?) and "reach" (e.g., were all nurses on the study units aware?), facilitators/barriers to implementation, mechanisms of action (e.g., did nurses respond to providing input, receiving guidance on how to report, or emphasizing near misses?), exposure to the SAFE Loop in the control arm, and contextual factors that may have moderated its effectiveness. Finally, we will discuss how to adapt the SAFE Loop for ongoing use over the long term and how to enhance its effectiveness.

B. Analysis: Interviews will be transcribed from audio recordings, with personal identifiers removed. Pairs of researchers trained in qualitative analysis will analyze transcripts in Dedoose using a combination of content-analysis and qualitative inquiry, allowing them to discover and quantify the nurses' experiences and perceptions. We will use an iterative process to identify *a priori* themes based on the domains above, and to create *in vivo* themes as they emerge during coding (e.g., specific barriers to implementation).⁶⁵ The two coders will code each interview independently and then discuss variations until consensus is reached. After coding all interviews, we will use the constant comparative method to combine similar themes with limited data under more general themes.⁶⁶ In the final step of analysis, we will review Dedoose code reports (participant N and density) of salient themes and coding matrices related to significant interview findings.

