5 STUDY POPULATION

5.1 INCLUSION CRITERIA

Study Nursing Units:

The study will include 34 acute care areas within Cedars-Sinai medical Center, which are grouped together into 20 nursing units by virtue of sharing the same nursing unit manager (**Table**). To facilitate blocked randomization, we grouped similar nursing units together into 5 blocks with four nursing units per block. The four nursing units within each block are as similar as possible (e.g., medical units are grouped together, ICUs are grouped together, etc.).

Table: Study Nursing Units, Patient Populations, Type, Size, & Allocation to Blocks						
	Unit Areas	Typical Patient Population	Type	Nurses	Pt-Days*	
Block 1: Larger medical floor units						
A	4SE, 4SW	Adult oncology	Floor	118	22,322	
B	5NE, 5NW	Cardiology	Floor	116	21,534	
C	5SE, 5SW	Adult medicine, gastroenterology	Floor	103	22,025	
D	7SE, 7SW	Adult medicine	Floor	92	22,025	
Block 2: Smaller medical floor units and emergency department						
A	6SE, 6SW	Congestive heart failure	Floor	104	18,552	
B	ED	Emergency department (ED)	ED	167	19,108	
C	3-SCCT	Medicine, congestive heart failure	Floor	50	10,188	
D	3NW	Short stay medical	Floor	41	2,437	
Block 3: Surgical floor units						
A	6NE, 6NW 6ICU	Kidney & liver transplant, cardiac surgery, Post cardiac-catheterization recovery	Floor, ICU	122	21,493	
B	7NE, 7NW	Med/surg orthopedics	Floor	106	20,901	
C	8SE, 8SW	Med/Surg bariatrics, GI surgery	Floor	100	15,230	
D	8NE, 8NW	Neurosurgery, Med/surg spine	Floor	78	15,230	
Block 4: Adult intensive care units						
A	4N-SCCT, 6-SCCT	Cardiac ICU, Cardiothoracic surgery ICU	ICU	130	10,711	
B	5-SCCT	Surgical and trauma ICU	ICU	91	6,381	
C	7-SCCT	Respiratory/medical ICU	ICU	69	7,085	
D	8-SCCT, 4NW	Neurosurgical ICU, Adult stroke/medicine	ICU, Floor	124	17,424	
Block 5.1: Obstetric and postpartum units						
A	3NE	Maternal-fetal care (obstetrics)	Floor	123	14,486	
B	3SE, 3SW	Post-partum	Floor	115	13,476	
Block 5.2: Pediatric units						
C	4S-SCCT, 4NE	Pediatric and congenital cardiac ICU, Pediatrics	ICU, Floor	44	3,903	
D	4NICU	Neonatal ICU	ICU	87	9,959	
*Patient-days of care on nursing unit per year.				Total	1980	294,470

Nurses:

- Aims 1 & 3 (SAFE Loop Incident Reports and Medical Record Review): All 1,980 nurses on the nursing units will be eligible to participate in the SAFE Loop and therefore participate in Aims 1 and 3.

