6.3 MEASURES TO MINIMIZE BIAS: RANDOMIZATION AND BLINDING

Random Sequence Generation, Allocation Concealment, and Blinding: A researcher (not on the SAFE Loop or Data Collection teams) will use computer-generated random numbers to randomly assign the 4 nursing units within each of the 5 randomization blocks to one of 4 study groups, reflecting 2 arms (intervention and control) and 2 periods of time (sequential implementation; see Table below). Next, the researchers will place lists of the nursing units assigned to each group in opaque, sealed envelopes labeled with group numbers. At the start of each implementation period, the SAFE Loop Team will open the corresponding envelopes to determine the 5 nursing units that are assigned to each group. Research staff involved in data collection will be blinded to which nurses and patients are assigned to which arm.

Table: Study Design, Including Study Arms and Measurement Periods								
Group	½ Year 1		Year 2			Year 3		
1	Baseline	b	SAFE Loop	f	i	Follow-on		
2	Baseline	b	Control	f		Follow-on		
3			Baseline	b	SAFE Loop	f	i	Follow-on
4			Baseline	b	Control	f	Follow-on	
Light green = baseline measurement periods for Aims 1 & 3								
Orange = baseline (b) and follow-up (f) survey deployments for Aim 2								
Dark blue = SAFE Loop arm								
Medium blue = control arm								
Yellow = qualitative interviews (i) on implementation and follow-on period								
Dark green = follow-on period for Aim 3								

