9.3 POPULATIONS FOR ANALYSES

The trial will randomize 20 nursing units to two arms: (1) the SAFE Loop, and (2) the existing reporting system (control). All analyses will compare data between these two arms.

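### Aim 3 drops the emergency department, yet Table 3 and the 147-event figure appear to include it, and no rule says whether an ED-chosen target counts

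*Combined protocol and SAP*

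**What the plan says.** - Section 8.1, Aim 3 Data Collection: "We will exclude the emergency department from Aim 3". The same paragraph sets the sample: "we will randomly sample 1,520 hospitalizations divided equally between the four study groups and the baseline and follow-on periods".
- Section 8.1, Aim 3 Measures, defines the primary outcome by the Target Medication Events "selected by the 10 nursing units in Groups 1 and 3", with no exception for the ED. The descriptive measures there also record, for each event, which intervention unit's target it matches.
- Section 5.1 lists the ED as a unit in "Block 2: Smaller medical floor units and emergency department", with 167 nurses and 19,108 of the 294,470 yearly patient-days. It also counts all 1,980 nurses as taking part in Aims 1 and 3. Section 5.2 (exclusions) does not name the ED.
- Section 6.3 assigns the four units in each block "to one of 4 study groups, reflecting 2 arms (intervention and control) and 2 periods of time". Section 9.3 states: "The trial will randomize 20 nursing units to two arms".
- Section 9.2 gives Table 3 (80% power, two-sided 5%) and calls a difference of 0.50 per 1000 patient-days meaningful, equal to 147 events a year hospital-wide. It prints no cluster count, baseline rate or exposure for Aim 3.

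**The concern.** The exclusion takes one cluster out of Aim 3, but nothing downstream is visibly adjusted for it. Two things follow.

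First, if the detectable differences were computed on all 20 units, they describe a design that Aim 3 will not have. The loss is greatest where results are reported by implementation step, because one arm of the ED's step falls from five units to four.

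Second, each intervention unit chooses its own target, and H3.1 pools those targets over all sampled units. If the ED is an intervention unit and its target stays in the numerator, the trial would count an event type whose only treated unit supplies no charts. Those events add counts to both arms with no unit-specific effect to detect.

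**Working it through.** **Formula.** The cluster-trial formula for Poisson rates (Hayes–Bennett), allowing unequal arms, with d the detectable difference, r0 the control rate, r1 the intervention rate, y the exposure per unit-period, k the between-cluster CV, and c0, c1 the clusters per arm:

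d² = K × { (r0/y + k²r0²)/(c0 − 1) + (r1/y + k²r1²)/(c1 − 1) }, with K = (1.960 + 0.842)² = 7.849.

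**Check on Table 1, where Section 9.2 prints the inputs.** Using r0 = 2.26 and y = 7.362 (thousand patient-days), or r0 = 0.70 and y = 16.6 (reports), with r1 = r0 + d, all 16 cells return within 0.001 at c = 10 per arm (no trend) and c = 5 (trend).

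**Reproducing Table 3.** Here r1 = r0 − d. Rate and exposure must be back-solved. With c = 10 and 5, the two outcomes separately give y = 38.05 and 37.96. That matches 1,520/(20 units × 2 periods) = 38. Fixing y = 38, with r0 = 5.95 (3.1) and 1.16 (3.2), returns all 16 cells within 0.001. Example, 3.1 without trend at CV 0.01:

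- r0 term: 5.95/38 + 0.0001 × 5.95² = 0.1601
- r1 term (r1 = 5.433): 0.1430 + 0.0030 = 0.1459
- d = √[7.849 × (0.1601 + 0.1459)/9] = 0.517 (printed: 0.516)

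Other cluster counts fit less well: 9.5/4.75 per arm misses by up to 0.23%, 9/4.5 by 0.40%, and 9/4 by 4.2%.

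**Events per year.** 0.50 × 294.470 = 147.2, the stated 147. Without the ED: 0.50 × (294.470 − 19.108) = 137.7.

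**On 19 units.** One arm loses a cluster: 9 v 10 without trend, 4 v 5 in the ED's step. Example, ED in control, y = 38, CV 0.01, no trend: d = √[7.849 × (0.1601/8 + 0.1455/9)] = 0.533. The ranges below cover the ED in either arm, with y = 38 (ED records lost) or y = 1,520/(19 × 2) = 40 (total kept).

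| Row | CV | Table 3 | 19 units |
|---|---|---|---|
| 3.1 no trend | 0.01 | 0.516 | 0.519–0.533 |
| 3.1 no trend | 0.20 | 1.474 | 1.500–1.526 |
| 3.1 trend, ED step | 0.01 | 0.766 | 0.802–0.830 |
| 3.1 trend, ED step | 0.20 | 2.108 | 2.190–2.311 |
| 3.2 no trend | 0.01 | 0.220 | 0.220–0.227 |
| 3.2 no trend | 0.20 | 0.340 | 0.344–0.352 |
| 3.2 trend, ED step | 0.01 | 0.322 | 0.334–0.350 |
| 3.2 trend, ED step | 0.20 | 0.486 | 0.501–0.533 |

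Over all four CVs and relative to the reproduced values, 3.1 rises by 0.4–3.5% without trend and 3.9–9.6% with trend; 3.2 rises by 0.2–3.5% and 3.1–9.7%.

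**Chart allocation.** An equal split gives 1,520/(4 × 2) = 190 records per group-period, so 190/5 = 38 per unit, but 190/4 = 47.5 in the group that loses the ED. Taken literally (y = 47.5, c = 4 in that arm of the step), the 3.1 trend difference becomes 0.779–0.781 at CV 0.01 (about 2% up) and 2.19–2.30 at CV 0.20 (about 4–9% up). The size of the loss therefore depends partly on an allocation the plan leaves open.

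**ED target.** Two of the four groups are intervention groups, so P(ED in SAFE Loop) = 2/4 = 1/2. In that case 10 targets are counted under the literal definition, and 9 have their own treated unit in the Aim 3 data.

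**The case against.** The strongest reply is that excluding the ED from Aim 3 naturally removes its target as well, and that the reference to 10 units is only a label for the arm. Because each event is coded to the unit whose target it matches, an ED target can be dropped at analysis without new data. This stands in part: a reader might infer that the ED's target will certainly be counted, and the documents do not support that. They support only that no rule settles it.

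Nor can one target in ten be read as 10% dilution. How often ED-chosen events occur on inpatient units is not given, and pooling already means that most targets counted on any unit were chosen by other units. A reader might also suspect bias toward benefit. The exclusion is fixed by unit type, not by arm, so it brings imbalance and possible dilution instead.

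On power, the 20-unit basis is inferred, not printed, and 1,520 also divides evenly over 19 units (40 each). That is fair, but the fit at 10/5 and 38 is the closest of those tried, and the 147 figure independently includes ED patient-days. It is also fair that the no-trend loss is small: for a 0.50 drop in 3.1 at CV 0.05, power goes from 59.7% to 57.0–58.7%, and every 3.1 cell already exceeds 0.50. This point does not show that Table 3 is badly wrong, only that it describes one unit too many.

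**Conclusion.** The point holds as a minor inconsistency. Aim 3 has 19 units, while its stated detectable differences and yearly event count match a 20-unit design. The correction to 3.1 is about 0.4–3.5% without trend and about 4–10% with trend in the ED's step; the latter is nearer 2% at CV 0.01 if the group left with four units keeps its full 190 records. These sizes rest on back-solved baseline rates (5.95 and 1.16), an inferred cluster count, and the normal-quantile formula that reproduces the table. The uncounted-for ED target is conditional: it needs the ED to be randomised to SAFE Loop and the outcome definition to be applied literally. Its effect would be dilution of H3.1, of a size the documents do not allow to be estimated.

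**What to change.** 1. Define the H3.1 and H3.2 numerators as Target Events chosen by intervention units that contribute Aim 3 charts. The planned coding by unit already permits this.
2. State in Sections 5.1, 8.1 and 9.3 that Aim 3 has 19 units, 9 v 10 by arm and 4 v 5 in the ED's step, and correct the statement that all 1,980 nurses take part in Aim 3.
3. State how the 190 records per group-period are spread in the group left with four units.
4. Recompute Table 3 on 19 units, printing the cluster count, baseline rates and exposure, and restate the 147-event figure and its harmful-event companion without ED patient-days. Confirm the unit of exposure while doing so: the fitted 38 equals the number of hospitalisations per unit-period, whereas the rates are per 1000 patient-days.

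The cost is a few sentences and one recomputed table. No new data or design change is needed. On the inputs that reproduce Table 3, the restated figures will be slightly less favourable. The numerator rule should be fixed before outcome data are seen by arm.
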